3.6.9 Study withdrawal criteria

The following criteria should determine the immediate withdrawal of the volunteer from the study:

- Grade 2 or greater kidney abnormalities at any time of follow-up.
- Clinical indication to start a drug with significant interactions with TDF/FTC during the development of the study.
- Presentation of any serious adverse event related to the intervention, defined by the physicians assigned to the study.
- Any Adverse Event (AE) that determines that the volunteer wishes to interrupt the intervention.
- That the volunteer voluntarily and for any reason decide to withdraw from the study.

If any of the previously mentioned criteria are met, the doctor assigned to the study in charge of the follow-up will immediately inform the coordinator of their respective center. The report of all AE will be made by the principal investigator of each center, in accordance with the INVIMA regulations and taking into account the Standardized Operating Procedures (SOP) established by the study.

In the event that the patient withdraws their consent, no additional monitoring will be possible. This situation will be reported immediately to the clinical monitor and monthly to the Institutional Research and Ethics Committee (CIEI).

3.6.10. Follow-up of volunteers with a positive pregnancy test at the end of follow-up

Despite the fact that TDF/FTC is a classification B drug in pregnancy, and its use is recommended as one of the antiretrovirals of choice in pregnant women with HIV (76), within this study it was defined to exclude pregnant women, or with the desire to become pregnant, to avoid exposure to this drug given its high placental transfer to the fetus.

There is no evidence in humans of teratogenicity with TDF/FTC, however there is evidence in monkeys, at doses twice as high as the therapeutic doses in humans, of decreased fetal growth and reduced fetal bone porosity within two months of initiation of maternal therapy; Regarding human studies, there is no demonstrated relationship with low birth weight, but there are conflicting results on the outcome of growth in childhood (77).

In a randomized, double-blind, placebo-controlled trial of PrEP in African women, Mugo NR, and colleagues (78) evaluated the effect of TDF/FTC on pregnancy for HIV-uninfected women. Differences in the incidence of pregnancy, delivery outcomes, and infant growth were not statistically different for women who received PrEP with TDF alone, or combination of FTC + TDF compared to placebo at conception. Considering that PrEP was discontinued when pregnancy was detected and that the confidence intervals for delivery outcomes were wide, the authors did not commit to making definitive statements about the safety of PrEP in the period of periconception (78).

For the above reasons, if any volunteer presents a pregnancy at the end of the intervention period, a specific Informed Consent Form will be filled out to carry out a follow-up during the pregnancy.

4. Statistical analysis plan

Initially, a descriptive analysis of the information will be made, and measures of central tendency and dispersion will be reported according to the type of variables. In this phase, the similarity between the groups of the experiment will be evaluated and it will be calculated if there are differences in the groups due to chance.

Primary outcome

Taking into account that this study is a pragmatic clinical experiment, which will evaluate effectiveness, an intention-to-treat analysis will be carried out, to solve the main objective, the proportion of incidence of SARS-CoV-2 infection in each group will be determined at the day 75 post-randomization, estimated as the cumulative incidence of infection using the Kaplan Meier method.

Exposure of interest: Prophylaxis with TDF/FTC plus EPP vs placebo plus EPP.

Primary outcome: SARS CoV2 infection

Zero follow-up time (registration time in the registry): the time that the volunteer is randomized to the study interventions.

Follow-up time: All individuals have a follow-up until they present the primary outcome, or meet any of the withdrawal criteria, or up to 75 days after the zero follow-up time, if they do not present the outcome.

Event: SARS-CoV-2 infection.

Censorship: censorship occurs when the outcome is not presented, the two types of censorship will be: administrative censorship 75 days after randomization, or censorship for compliance with any of the criteria for withdrawal from the study, or loss of follow-up.

The hazard ratio will be estimated by comparing the risk of infection in the intervention group (TDF/FTC + EPP), with the risk in the control group (placebo + EPP), with a confidence interval of 95 %, using a univariate Cox regression model.

If necessary, adjustment will be made for variables that may affect the occurrence of the primary outcome and that are not balanced between the intervention group and the placebo group; The need for adjustment with an OR greater than 1.5 will be considered for dichotomous categorical

variables, such as sex; or if there are differences between the groups greater than 0.25 of the standard deviation for continuous variables such as age, adherence to pharmacological intervention or EPP, and hours of exposure to the COVID area. For the calculation of the adjusted hazard ratio, a multivariate Cox proportional hazards model will be used, if the proportionality assumption is met, or an extended Cox model if this assumption is not met.

For secondary outcomes

-The proportion of incidence of total adverse effects in each group will be determined at day 60 after randomization, estimated as the cumulative incidence using the Kaplan Meier method.

The hazard ratio ("Hazard Ratio") will be estimated by comparing the risk of adverse events in the intervention group (TDF/FTC + EPP), with the risk in the control group (placebo + EPP), with a confidence interval of 95%, using a univariate Cox regression model.

Additionally, the same analysis will be performed for serious adverse events.

- The proportion of incidence of discontinuation of the intervention in each group, for any reason, will be determined at day 60 after randomization, estimated as the cumulative incidence using the Kaplan Meier method.

The hazard ratio will be estimated by comparing the discontinuation of the intervention in the intervention group (TDF/FTC + EPP), with the risk in the control group (placebo + EPP), with a confidence interval of 95 %, using a univariate Cox regression model.

- It will be determined as the difference in the mean or median (according to the distribution of the data) of the percentage in which the individuals were adherent

-For the severity of the clinical course of the patients who develop the infection in both groups, a descriptive analysis will be carried out, the quantitative variables will be summarized by measures of central tendency and dispersion, according to the most appropriate measures for their distribution. The qualitative variables will be summarized by using absolute and relative frequencies (proportions) represented by percentages.

4.1 Data and Security Surveillance Committee:

A data and safety surveillance committee (DSSC) is defined as a group of experts, independent of the sponsor and investigators, who monitor the safety and validity of clinical trials. The committee carries out surveillance activities during established time intervals, in which, in addition to the safety data, the adequate recruitment of volunteers, compliance with the protocol, and the quality of the data obtained are evaluated (79).

A review of the literature by Sydes and colleagues (80) found that a DSSC is recommended when trials have any of the following characteristics: trials on high-profile topics that are a focus of community concern, to be used to search regulatory approval, or likely to profoundly affect clinical practice; trials with serious safety problems, unknown risks or that are implemented in vulnerable populations; and trials where independent monitoring is needed due to double-blind treatment allocation or long-term follow-up or because the sponsoring company does not have standard operating procedures. These authors also consider that DSSC may not be needed for trials of short

duration (where it is not feasible to convene a DSSC in a timely manner to review the data), for trials with known risks that are minimal, for trials where the objective is to demonstrate biological principles (as in early phase clinical trials) or for trials on behavioral or administrative problems.

In the case of this study, in favor of having a data and safety monitoring committee, it is found that the issue addressed in the research is of high concern to society, given the importance of health workers for the management of people with COVID-19 infection, but also the implications that demonstrating the effectiveness of this intervention in this population may have, to later be able to demonstrate it in other populations such as the elderly or the general population. However, the difficulty of conducting a data monitoring committee in this experiment lies in its short duration, with a collection of information in only four months, which makes it impossible, a timely review of it, which allows making decisions before. Upon completion of recruitment, on the other hand, TDF/FTC is not a new drug and there is extensive knowledge about its safety and tolerance, and based on this information, a large part of the inclusion and exclusion criteria of the present study have been included, therefore, frequent and serious safety problems are not expected (10-13)

For this reason, it has been decided that this clinical experiment does not have a data monitoring committee, for the reasons previously stated. To avoid deviations in the protocol, there will be an investigator's manual, in which the management of serious and non-serious adverse events is explicit, as well as their causality analysis, and a set of standard operating procedures (SOPs). that will be delivered, disseminated and knowledge will be guaranteed by each of the participating centers during the enlistment process, strict monitoring by each of the monitors of the centers will also be guaranteed during recruitment, with internal audits and with minus one external audit before the third month of recruitment for each center, which will evaluate the conduct of the study, adequate recruitment of volunteers, compliance with the protocol, investigator's manual, SOPs, good clinical practice, and data quality.

5. Risks and benefits for volunteers

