3.6. Procedures

In table 1. Detailed follow up evaluations are described.

Table 1. Description of the evaluations to be done during the trial.

Follow up table				
Day	General activity	Specific activity	Responsible	Result
0	Base line diagnoses	Initial Clinical evaluation	Medical doctor of the study	Evaluating inclusion and exclusion criteria. Signing informed consent form
		Blood samples	Nurse Lab tech	Laboratory report: hemogram, creatinine, phosphorus, AST, ALT HIV ELISA, HB Surface antigen antibodies
		SARS-CoV-2 RT-PCR sampling	Respiratory therapist or nurse	Result of SARS-CoV-2 RT-PCR
		SARS-CoV-2 IgM and IgG antibodies	Nurse Lab tech	Result of IgM and IgG antibodies
		b-HCG sampling in women	Nurse Lab tech	Report of b-HCG
20	Visit 1	Clinical evaluation	Medical doctor of the study	Clinical record and eCRF for clinical evaluation, adherence, and adverse events

40	Visit 2	Blood sample for: SARS-CoV2 IgM, IgG antibodies and blood chemistry	Nurse Lab tech	Laboratory report of SARS-CoV2 IgM, IgG antibodies and creatinine
		Clinical evaluation	Medical doctor of the study	Clinical record and eCRF for clinical evaluation, adherence, and adverse events
60	Visit 3	Blood samples	Nurse Lab tech	hemogram, creatinine, phosphorus, AST, ALT HIV ELISA, HB Surface antigen antibodies b- HCG in women
		SARS-CoV-2 RT-PCR sampling	Respiratory therapist	Result of SARS-CoV-2 RT-PCR
		Clinical evaluation	Medical doctor of the study	Clinical record and eCRF for clinical evaluation, adherence, and adverse events
75	Visit 4	Blood samples	Nurse Lab tech	Laboratory report of SARS-CoV2 IgG
		Clinical evaluation	Medical doctor of the study	Clinical record and eCRF for clinical evaluation,
		End of follow up and communication to study subject	Clinical coordinator	Minutes

During follow up to any participant who develop COVID-19 related symptoms at any time after randomization given by two or more of the following: Body temperature higher than 38 Celsius, cough of recent onset (in the previous 10 days), dyspnea,odynophagia, malaise, fatigue, acute diarrheal disease, ageusia, dysgeusia, anosmia or hyposmia, an RT-PCR will be performed within the next 5 days and will be repeat it if the result is negative and the symptoms persist. This RT-PCR will be performed at every of the centers of the study and will request the patient the immediate report of the symptoms through an app or via phone call. In case of a positive RT-PCR the infection

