will be confirmed. While confirmation RT-PCR arrives, the participant will not quit taking the intervention. In that scenario, the intervention will only be suspended in the case of a highly suspected case or severe case requiring hospitalization.

In case the infection is ruled out in the follow up, the participant will continue the interventions and follow up scheduled, according to graph 1.

With regards to diagnostic testing during follow up as shown in table 1. IgG antibodies will be done at visit 2 and 4 (40 days from initially taking the intervention and 15 day after finalizing it). This considering volunteer that might acquire the infection in the last days of the pharmacological intervention. Moreover, at day 60, last of the intervention, an RT-PCR will be performed to all participants. This in order to detect participants who develop asymptomatic infection. The research group is aware that this follow up will not identify a 100% of the asymptomatic infection for the low sensitivity of testing in this scenario, approximately 30 to 40% (46,47), yet it will be done in both arms.

Importantly, for the covid-19 emergency, clinical follow up, adverse event reporting and adherence reporting could be done online.

Personal Protective Equipment

All volunteers will be using the following personal protective equipment. This based on the guidelines of the WHO (23). See table 2.

Table 2. Use of PPE by study volunteers.

Area	Health care personnel or patients	Activity	Type of PPE or activity
Emergency room, general COVID wards or intensive care units	Health care workers	Direct contact with the patient of non-aerosol generating procedures.	Surgical mask Visor or glasses. Long sleeve gown Nonsterile gloves.
		Direct contact with the patient and aerosol generating procedures.	N95 respirator Visor or glasses. Long sleeve gown Nonsterile gloves. May dress

			under the robe that is removed at the end of the shift
Other areas of transit (hallways or waiting rooms)	All personnel including health care workers	Any activity that does not involve contact shorter than 2 meters in distance between people	Surgical mask

Adapted from: Rational use of personal protective equipment for coronavirus disease 2019 (COVID-19). Interim guidance 27 February 2020. World Health Organization. (23)

*Health care worker: person in whose activity directly care a contact, suspected, or confirmed case of COVID-19.

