5.1.1 Risks potentially associated with pharmacological intervention

TDF/FTC is considered a safe drug in the short term, and in periods of up to 2 to 3 years of use (81). In the studies of PrEP in HIV in which this drug is used as monotherapy, the systematic review by Fonner et al. (82) found no differences in the proportion of adverse events comparing TDF/FTC with placebo, in 10 randomized clinical trials (RCTs) controlled (OR 1.01, 95% CI 0.99 to 1.03, $p = 0.27$); It also found no differences in the subgroup analysis, according to adherence, gender, dose or age; nor in grade 3 or 4 adverse events when comparing the PrEP and placebo groups in 11 placebo-controlled RCTs (risk ratio = 1.02, 95% CI 0.92-1.13, $p = 0.76$).

The most common adverse effects reported with the drug are nausea, gastrointestinal (abdominal pain, bloating), and headache (77, 81). The use of TDF-FTC as PrEP has been associated with a mild non-progressive decrease in creatinine clearance (83), which is reversible on discontinuation of the drug (84).

An association has also been described between a decrease in bone mineral density (BMD) and the use of FTC-TDF for 24 weeks (84-87), but no evidence of an increased risk of fractures has been found, on the other hand, change in BMD did not progress after 24 weeks of use and recovered to levels seen in the placebo arm after stopping TDF/FTC (88-89).

Finally, there is a risk of severe acute exacerbations of hepatitis B in patients with hepatitis B virus (HBV) infection who discontinue TDF/FTC. Liver function should be closely monitored with clinical and laboratory follow-up for several months in HBV-infected patients who interrupt TDF/FTC, however, this phenomenon is rare, and the only evidence available is case reports. (90-92). In the present study, this risk will be avoided, because people with acute or chronic hepatitis B infection will be excluded and all volunteers will have immunity to hepatitis B, with anti-HBs greater than 10 IU/ml.

The following information presents, in more detail, the safety of TDF/FTC based on clinical, laboratory abnormalities, as well as alterations in bone mineralization and kidney function.

- Experience based on clinical experiments

Due to the control conditions of clinical trials, it is possible that the rates of adverse reactions that have been described do not necessarily reflect those observed in clinical practice and may be overestimated.

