A case report form will be created which must have the following information:

- Description of the adverse event
- Date of presentation, duration, and day of resolution.
- Severity according to degrees mentioned
- Conduct taken (need for treatment, suspension of medication, hospitalization)
- The probability of relationship with the drug under study.

All the follow-up of adverse events will be determined according to the Standardized Operational Plan for adverse events of the study.

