Telephone contact potential volunteers		X							Registration with participants interested in being included	Record of execution of the procedure and database in Excel.
Informed consent		X							Signed informed consents	Database of study subjects recruited
Clinical CRF history		X	X	X	X	X			Clinical History of the study subject	Clinical CRF Registry
Clinical Assessment		X	X	X	X	X			Clinical History of the study subject	Clinical CRF Registry
Supervised first dose of drug administration		x							Confirmation of taking at least 1 dose of TDF/FTC or placebo	Drug dispensing registration document
Taking of RT-PCR for SARS-CoV-2		X			X				Positive or negative diagnostic test result	Laboratory report
Antibody IgG - IgM SARS - CoV-2 testing		X		x		x			Positive or negative diagnostic test result	Laboratory report
Sampling for CBC, Creatinine, AST, ALT, P, HIV ELISA, Acs anti HBsAg and		X		X		X			Results of liver, kidney, hematological, electrolyte function tests and pregnancy status in the	Laboratory report

Beta HCG in women									case of participating women.	
Verification of eligibility criteria		X							Determination of the inclusion or not of the participant	Check list
Randomization		X							Random Assignments to Intervention or Placebo	Database
CRF Adverse Events Registry			X	X	X	X			History of adverse events	CRF registration document Adverse event
Finish follow-up and communication to the study subject							X		Formal follow-up completion record	Completion certificate document
Systematization and organization of data							X		Office registry refined with data extracted from the clinical trial	Systematized database
Results analysis								X	Outcome estimates, statistical associations, causality inferences and risks of bias and limitations	Document with results, tables, graphs and data of the study
Communication and publication of results and conclusions.								X	National and international communication of the results and	Two articles of scientific publication, report of results and recommendation

									conclusions of the study	ns of the researchers
--	--	--	--	--	--	--	--	--	-----------------------------	--------------------------

9. Budget

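### Table 6 puts the safety blood panel at visits 2 and 4, where Table 1 and the rest of the protocol put it at visit 3 (day 60); a lesser gap is that the protocol text names no safety draw at early study exit.

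*Combined protocol and SAP*

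**What the plan says.** Section 3.6 sends the reader to Table 1 for the evaluations. There, visit 2 has antibodies and creatinine. Visit 3, the last day of dosing, has "hemogram, creatinine, phosphorus, AST, ALT HIV ELISA, HB Surface antigen antibodies b- HCG in women". Visit 4 has IgG only.

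Table 6 (study schedule) has a row beginning "Sampling for CBC, Creatinine, AST, ALT, P, HIV ELISA, Acs anti HBsAg and" and ending with beta-HCG in women. It is marked at recruitment, visit 2 and visit 4.

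Section 3.6.9 (Study withdrawal criteria) introduces five criteria with "The following criteria should determine the immediate withdrawal of the volunteer from the study". It then requires that the centre coordinator be told and that adverse events be reported, and says that no monitoring is possible after consent is withdrawn. The other section numbered 3.6.9, on the primary outcome, stops product, releases the masking and provides telephone follow-up. Neither names a safety blood sample.

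On adverse events, section 6.2 states: "All the follow-up of adverse events will be determined according to the Standardized Operational Plan for adverse events of the study". Section 4.1 refers to an investigator's manual "in which the management of serious and non-serious adverse events is explicit". Neither document was available for this review, and Graph 1 is not shown.

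**The concern.** The two schedules cannot both be followed. Under Table 6 a site would miss the end-of-treatment blood count, liver enzymes, creatinine, phosphorus and pregnancy test. The timing matters most for creatinine: section 5.1.1 describes a mild fall in creatinine clearance "which is reversible on discontinuation of the drug", so a value taken 15 days after the last dose may understate what happened on drug.

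The exit gap concerns people who leave the study before day 60, some of them because of toxicity. Under Table 1 the only blood count, AST, ALT and phosphorus after baseline are at day 60, and the first creatinine is at day 40. Someone who leaves before those visits has no such result planned in the protocol text. Section 5.1.1 itself reports more grade 3 or 4 neutropenia on TDF/FTC than on placebo (4% against 2%) and one stop for low phosphorus. The trial has no data monitoring committee.

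**Working it through.** **1. Which schedule is right**

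| Source | Visit 2 (day 40) | Visit 3 (day 60) | Visit 4 (day 75) |
|---|---|---|---|
| Table 1 | creatinine, antibodies | full panel, RT-PCR | IgG |
| Table 6 | full panel, antibodies | RT-PCR | full panel, antibodies |
| Appendix 3 | creatinine, IgG | creatinine, blood count, AST, ALT, pregnancy test, RT-PCR | IgG |
| Budget, section 9.1 | item 4: creatinine, antibodies | item 6: creatinine, blood count, ALT, AST, beta-HCG, RT-PCR for all | item 7: IgG |

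Item 6 names no visit, but it includes RT-PCR for all subjects, which after baseline happens only at day 60.

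Section 3.6.10 acts "if any volunteer presents a pregnancy at the end of the intervention period", which again points to visit 3. This support is weaker, since that section's heading refers to the end of follow-up. Section 4 reads the cumulative incidence of adverse events at day 60, which also fits visit 3.

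A column shift in the extracted text is unlikely. In the same table the RT-PCR row (recruitment, visit 3) and the antibody row (recruitment, visits 2 and 4) both agree with Table 1. The original layout should still be checked.

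Appendix 3 also has no field for a blood count, AST or ALT at visit 2, or for any of the panel at visit 4. A site following Table 6 would therefore hold results with no specified place to record them.

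**2. How many leave early because of adverse events**

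The protocol gives no expected number. Section 5.1.1 cites an open-label PrEP cohort with 34 permanent stops among 1,225 users over a possible 1,784 person-years.

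- Not scaled for time: 34/1,225 = 2.8%; × 475 = 13.2 on active drug.
- Scaled to 60 days: 475 × 60/365.25 = 78.0 person-years; 34/1,784 × 78.0 = 1.5.

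Other exits, such as starting an interacting drug, are not sized in the documents.

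**3. Toxicity that could go unseen**

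- At 4% grade 3 or 4 neutropenia: 13.2 × 0.04 = 0.53 cases. The excess over placebo at 2 percentage points is 0.26.
- The 4% comes from a trial reported to 36 months. Assuming a constant hazard over that time, the 60-day risk is 1 − 0.96^(60/1,095.75) = 0.223%, and 13.2 × 0.00223 = 0.03 cases.

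**4. If infected participants also left the visit schedule (not stated)**

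The planning risks are 0.05 on active drug and 0.10 on placebo, with 475 per arm.

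- Read as 75-day risks with constant hazard: 1 − 0.95^(60/75) = 4.02%, or 19.1; 1 − 0.90^(60/75) = 8.08%, or 38.4; total 57.5.
- Read as 60-day risks: 23.75 + 47.5 = 71.25.

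So 57 to 71 of 950 would be an upper bound, because infections first found at the day-60 visit have that visit's draw.

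**5. Phosphorus**

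Table 1 draws it at day 60. Appendix 3 has no follow-up field for it, and Table 5 (laboratory abnormalities) has no row to grade it.

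**The case against.** Table 6 is a work plan, while sections 3.1 and 3.6 direct readers to Table 1. The panel row repeats the visit pattern of the antibody row above it, which suggests a clerical slip. That stands, and it makes actual harm unlikely. But Table 6 is still a schedule in the protocol and it is wrong as written.

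A reader might infer that a site following Table 6 would have no laboratory safety data on treatment. It would: a full panel at day 40, earlier than Table 1's first blood count and liver enzymes. What is lost is the end-of-treatment panel.

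A reader might also infer that the plan has no exit sample at all. The documents show only that the protocol text is silent; the adverse-event operating plan or the manual may require one. The group concerned is also small. A renal withdrawal already rests on a creatinine, no draw can be required after consent is withdrawn, and a related serious event falls under the adverse-event plan.

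The most tempting stronger reading is that everyone who stops product before day 60, including the infected, has no planned panel. Section 3.6 lends it some colour: "In case the infection is ruled out in the follow up, the participant will continue the interventions and follow up scheduled". Section 4 also ends primary-outcome follow-up at infection. But stopping product is not leaving the visit schedule. Nothing in Table 1 cancels day 60 for someone off product, and Appendix 3 records interruption separately. The 57 to 71 infections are therefore conditional and not part of the finding.

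On phosphorus, physicians review the results, and the adverse-event fields allow a free-text entry. What is missing is a dedicated field and a grade.

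**Conclusion.** Table 6 contradicts Table 1, Appendix 3 and the budget, and should be corrected. This part depends on no unseen document, only on the extracted table layout being right. Whether any site would follow Table 6 is unknown.

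The exit-draw gap is real in the protocol text but secondary. It covers about 1.5 to 13 adverse-event stops among 475 on active drug, plus exits that the documents do not size. Neutropenia missed would be at most about half a case, and about 0.03 with time scaling. These figures assume that the cited PrEP experience carries over to health care workers.

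The adverse-event and serious-adverse-event hazard ratios are negligibly affected, since someone who leaves for toxicity already counts as an event. The gain is a safety check for the individual and complete end-of-treatment laboratory data. Severity: minor.

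**What to change.** 1. Correct Table 6 to match Table 1: full panel with beta-HCG at visit 3, creatinine alone of the panel at visit 2, and IgG only at visit 4.
2. In section 3.6.9 and Table 1, take the visit-3 panel, including beta-HCG, from anyone who leaves the study before day 60, except on withdrawal of consent, and record its date. If the operating plan or manual already requires this, cite it instead.
3. For those who stop product but stay in follow-up, keep the day-60 visit and panel, and say that this includes infected participants. An early draw should not replace the day-60 panel in this group, because planned data and the pregnancy test would be lost. Report any draw taken during acute infection separately: it follows unmasking and, under the planning risks, would occur about twice as often on placebo (0.10/0.05).
4. Add a follow-up phosphorus field to Appendix 3 and a phosphorus row to Table 5 (laboratory abnormalities).

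The cost is wording, one table and small changes to the case report form. For people who leave early, the exit draw takes the place of a day-60 draw that would not happen. Budget item 6 already covers its blood count, creatinine, AST, ALT and beta-HCG. Item 6 does not name phosphorus, while item 2 names it for baseline and follow-up, so its day-60 funding needs checking. The downside is an occasional unscheduled draw.
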